6.6 Safety parameters and analysis

Safety and tolerability assessments include AEs, vital signs (blood pressure, heart rate, body temperature), blood glucose (fasting plasma glucose, Hemoglobin A1c), hormones (IGF -1, TSH/free T4), liver enzymes (AST, ALT, alkaline phosphatase, γ GT, total bilirubin), hematology, electrolytes, gallbladder ultrasound and ECGs.

All the safety analysis will be over core and extension phase combined based on safety set.

6.6.1 Adverse events (AE)

All adverse events and the cause of death, as recorded on the completion CRF pages, will be coded using the latest available version of the MedDRA coding dictionary that provides the system organ class (SOC) and preferred term (PT) information.

AEs will be graded according to the Common Terminology Criteria for Adverse Events (CTCAE) version 4.0.

The CTC/severity grade will not be imputed if missing. CTC grade 5 (death) will not be used in this study.

The incidence of treatment-emergent AEs, during the core phase and during the overall on- treatment period, will be summarized by system organ class (SOC), preferred term (PT) and severity (based on NCI-CTCAE v.4 grades), type of adverse event, relation to study treatment.

A patient with multiple occurrences of an AE will be counted only once in the respective AE category

The following selection of treatment-emergent AEs will be listed and summarized for safety set from study start to final cut-off date for safety set:

- AEs regardless of study drug relationship
- AEs suspected to be study drug-related
- SAEs regardless of study drug relationship
- AEs leading to study drug discontinuation, regardless of study drug relationship
- AEs leading to study drug discontinuation, suspected to be study drug-related
- AEs requiring dose adjustment or study-drug interruption, regardless of study drug relationship
- AEs requiring additional therapy, regardless of study drug relationship
- AEs excluding SAEs
- Adverse events of special interest by type

Specific groupings of AEs of special interest will be considered and the number of patients with at least one event in each grouping ("category") will be reported. Such groups consist of AEs for which there is a specific clinical interest in connection with pasireotide treatment (i.e. where pasireotide may influence a common mechanism of action responsible for triggering them) or AEs which are similar in nature (although not identical) within safety set. The specific groupings of AEs as defined in the latest documentation available prior to database lock (in [[Cabinets/CREDI Projects/S/SOM230B/Integrated Medical Safety/Safety Profiling and Signal detection/Signal detection]]).

The following table will be produced:

- AEs of special interest by type (any AE, AE suspected to be drug-related, SAE, AE leading to discontinuation, AE requiring dose adjustment), PT and maximum Common Terminology Criteria (CTC) grade.

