### **Extension phase**

After up to 35 weeks of treatment, patients have the option to continue study treatment if pasireotide is not approved for commercial use and/or reimbursed in each respective country, if country reimbursement is applicable. Patients can continue with study treatment on extension phase until pasireotide is approved for commercial use and reimbursed in their respective country, or until 31st December, 2019, or once an applicable roll over protocol becomes available, or whichever occurs first.

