## **10 Statistical methods and data analysis**

This is a phase II exploratory study to assess the efficacy and safety of pasireotide s.c. alone and in combination with cabergoline in patients with Cushing's disease.

The data will be analyzed by Novartis and/or designed CRO. It is planned that the data from all centers that participate in this protocol will be used.

Two separate analyses will be made one related to the core phase and one related to the overall phase, including the core and the extension phases.

Continuous variables will be summarized by number of patients, mean, standard deviation, minimum, 25th quantile, median, 75th quantile and maximum. Categorical variables will be summarized by absolute and relative frequencies.

Unless otherwise stated, baseline assessment refers to the last assessment prior to the patient's first study drug dose recorded after the signing of the informed consent.

In addition to the statistical methods outlined, further details and any additional exploratory analyses that may be performed will be described in the Statistical Analysis Plan (SAP).

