5.2 Safety set

Safety set: includes all patients who received at least one dose of study medication defined in the core and extension study phase.

The safety set will be used to combine the core and extension phase data for all safety analyses and summaries over the visit window with available data. Core phase data will be

summarized from baseline to week 35 at end of the core phase. Extension phase data will be summarized from week 43 to last cutoff week for patients enrolled into extension phase.

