6.4.1.1.2 Dose exposure and intensity

Dose intensity of cabergoline will be calculated for each patient as total cumulative dose at the time of last administration divided by the duration of exposure.

Duration of exposure and dose intensity while in the study will be summarized with descriptive statistics over the core phase. A frequency table will show the number and percentage of patients per duration of exposure category: core phase category (≤ 8 weeks, >8 to 17 weeks, >17 to 35 weeks, >35 to 40 weeks). For core and extension phase: (≤ 8 weeks, >8 to 17 weeks, 17-35 weeks, >35 to 43 weeks, >43 to 98 weeks, >98 to 153 weeks, >153 to 208 weeks, >208 to 263 (up to final week)).

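### Overall on-treatment AE percentages pool very unequal follow-up, and the SAP plans no patient-years or incidence by time interval to read them with

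*SAP*

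**What the plan says.** SAP 6.6.1 plans AE summaries for two windows: "The incidence of treatment-emergent AEs, during the core phase and during the overall on- treatment period". The listed selections (all AEs, SAEs, AEs leading to discontinuation, AESIs and others) are to be "listed and summarized for safety set from study start to final cut-off date for safety set". The counting rule is: "A patient with multiple occurrences of an AE will be counted only once in the respective AE category".

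The denominator is the safety set, which "includes all patients who received at least one dose of study medication defined in the core and extension study phase" (SAP 5.2). SAP 6.6 adds: "All the safety analysis will be over core and extension phase combined based on safety set". That the figures are percentages follows from Protocol section 10, "Categorical variables will be summarized by absolute and relative frequencies", and from Protocol 10.3.1.2, which asks for number and percentage of patients with an AESI.

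Protocol 10.3.1.1 runs the on-treatment period from first dose to 28 days after last dose, so its length differs by patient. SAP 6.4.1.1.2 and 6.4.2.1.1 tabulate exposure in categories that start at 8 weeks or less and end with ">153 to 208 weeks, >208 to 263 (up to final week". Protocol 6.2.2 makes the extension optional and ties it to the local market: "Patients can continue with study treatment on extension phase until pasireotide is approved for commercial use and reimbursed in their respective country", subject to a calendar limit or a roll-over protocol.

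Neither document, as supplied, plans patient-years at risk, exposure-adjusted rates, time to first AE or AE incidence by time interval. Exposure is reported separately and is not linked to the AE tables.

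**The concern.** A percentage with at least one event estimates a risk only over a stated period. Here the period could be a few weeks for one patient and five years for another, and the pooled figure is an average over whatever mix of durations occurred. For any event that continues to arise on treatment, longer retention raises the percentage even when the underlying rate is unchanged.

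The core-phase table does not have this problem to the same degree, because follow-up there is capped near 35 weeks. It cannot stand in for the overall table, however. Protocol Amendments 3 and 4 give longer-term safety and efficacy data, alongside continued access, as reasons for prolonging the extension, and the overall table is the main AE output for that purpose. As planned, it cannot be set against the core-phase figure or another study's figure without knowing the person-time. Nor can it show whether the incidence of an AE group rises, stays flat or falls with time on treatment.

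**Working it through.** **Inputs from the documents.** Exposure categories for core plus extension have boundaries at 8, 17, 35, 43, 98, 153, 208 and 263 weeks (SAP 6.4). The core phase lasts 35 weeks and planned enrolment is 64 (Protocol 4.1 and 5). The plan states no AE rate, so there is no figure of its own to reproduce beyond the spread: 263/8 ≈ 33-fold, 263/35 ≈ 7.5-fold, and 263/52.18 ≈ 5.0 years.

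**Assumed inputs.** The documents give neither event rates nor the share of patients entering the extension, so both are assumptions. The 28 days after last dose are ignored.

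**Step 1: same rate, different durations.** Under a constant rate r per patient-year, the chance of at least one event by week w is 1 − exp(−r·w/52.18).

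| r | 8 wk | 35 wk | 153 wk | 263 wk |
|---|---|---|---|---|
| 0.1 | 1.5% | 6.5% | 25.4% | 39.6% |
| 0.2 | 3.0% | 12.6% | 44.4% | 63.5% |
| 0.3 | 4.5% | 18.2% | 58.5% | 78.0% |

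**Step 2: same rate, different retention, N = 64.** In every mix 13 patients stop at 8 weeks. The rest are:
- Mix A: 38 at 35 weeks, 13 at 98.
- Mix B: 19 at 35, 16 at 98, 16 at 208.
- Mix C: 6 at 35, 20 at 153, 25 at 263.

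The crude percentage is the average of Step 1 over the mix. The exposure-adjusted rate is expected first events divided by patient-years to first event or end of exposure. For mix A at r = 0.1, expected events are 0.20 + 2.47 + 2.23 ≈ 4.89, and 4.89/64 = 7.6%. Person-time is 48.9 years, so the rate is 10.0 per 100 patient-years.

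| r | Mix A | Mix B | Mix C | Rate per 100 patient-years, all mixes | Core-phase %, all mixes |
|---|---|---|---|---|---|
| 0.1 | 7.6% | 14.7% | 24.3% | 10.0 | 5.5% |
| 0.3 | 20.5% | 34.5% | 51.4% | 30.0 | 15.4% |

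**Step 3: does an overall rate cure it?** Follow-up was simulated for 2 million patients. Extension entrants stay until a uniform time between weeks 43 and 263. The others are followed to week 35, except that 35% of them stop uniformly between weeks 4 and 35. Two event patterns were tried: a constant 0.2 per patient-year, and an early-onset event with 40% risk, all within the first 13 weeks.

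| Entering extension | Constant: crude | Constant: overall rate | Early: crude | Early: overall rate |
|---|---|---|---|---|
| 30% | 20.3% | 20 | 39% | 48 |
| 50% | 26.7% | 20 | 39% | 36 |
| 80% | 36.3% | 20 | 40% | 26 |

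Rates are per 100 patient-years. For continuing events the crude percentage moves with retention. For early events the single overall rate moves instead.

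**Step 4: rates by interval.** With intervals 0–17, >17–35, >35–98 and >98 weeks, the constant pattern gives about 20 per 100 patient-years in every interval at all three retention levels. The early pattern gives about 164 in the first interval and 0 afterwards, again at all three levels. Only the interval presentation is stable under both patterns.

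**The case against.** **Planned summaries already show part of the time course.** SAP 6.6.4 gives ECG values and changes at every scheduled time point to cut-off, and notable QT values for the extension separately. SAP 6.6.2 gives laboratory shift tables over core and extension. SAP 6.5.2 gives serum cortisol and mUFC by visit. A reader might infer that nothing in the plan can show how hyperglycemia, QTc or cortisol risk evolves; that is too strong. What stands is narrower: these are measurements, and the AE, SAE and discontinuation tables have no time dimension beyond core versus overall.

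**Event types can be compared.** A reader might infer that percentages for different events in the overall table are not comparable. They share the same patients and follow-up, so they are comparable as cumulative frequencies.

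**Follow-up is not set by reimbursement alone.** Protocol 7.1.2.1 requires withdrawal for toxicity, uncontrolled diabetes, QTc and hepatic criteria, and lack of efficacy. Protocol 2.1 reports that 48% completed 12 months in the pivotal study, with insufficient effect the main reason for stopping. Duration is therefore partly administrative and partly related to outcome, and censoring at discontinuation may be informative for any rate.

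**Separation by phase may be intended.** SAP 5.2 says extension data are summarized from week 43 for patients who entered the extension. SAP 6.6.1 names no extension AE table, so this is ambiguous.

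**The trial is single-arm and exploratory, and part of the SAP material is not available.** There is no between-arm comparison to bias. The core-phase SAP and SAP sections 8.2.6 and 8.3.2 are cited but not in the supplied text, so a method there cannot be excluded; nothing in 6.6.1 points to one.

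**Conclusion.** The point holds as a limit on interpreting the long-term AE figures. For events that keep occurring, the overall on-treatment percentage depends on how many patients stayed and for how long. In the illustrations it roughly triples (7.6% to 24.3%) or more than doubles (20.5% to 51.4%) across retention mixes with no change in the true rate. Those sizes rest on assumed rates, a constant hazard and assumed mixes. The 263 weeks is a table boundary, not an observed exposure.

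Two stronger readings are not supported. The crude percentage is not misleading for every event: where onset is confined to the first weeks it barely moves with retention. Nor is one exposure-adjusted rate a general remedy, since for early-onset events it is the figure that moves (48 to 26 per 100 patient-years in Step 3). The part of the remedy that survives both cases is incidence by time interval. This is an inexpensive improvement to a descriptive analysis, not a defect that invalidates the planned tables.

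**What to change.** In SAP 6.6.1, keep the planned counts and percentages and make these additions:

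1. Give total patient-years at risk with the overall on-treatment tables.
2. For AESI groups, SAEs and AEs leading to discontinuation, give first-event rates per 100 patient-years in a few broad intervals collapsed from SAP 6.4, for example 0–17, >17–35, >35–98 and >98 weeks from first dose. Show patients at risk in each interval. Count person-time to first event or end of the on-treatment period (last dose + 28 days).
3. If a single overall exposure-adjusted rate is also shown, state that it assumes a constant hazard, can mislead for early-onset events, and may be affected by informative discontinuation.
4. State whether a separate extension-phase AE table is intended under SAP 5.2.
5. If this is added after database lock, label it with its date. The SAP already carries a dated post-lock addendum for Karnofsky status.

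**Cost.** No new data are needed: dosing and AE dates are collected. There is some programming, because SAP 6.4 durations stop at last dose and person-time must be derived per event group. Tables become wider, and late intervals will be sparse. Under Step 3 with 30% entry, about 64 × 0.30 × (263 − 98)/(263 − 43) ≈ 14 patients would still be on treatment at week 98. That is why only a few broad intervals are proposed, and only for the key event groups.

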8. To assess the improvement of health-related quality of life	8. Change from baseline in standardized scores, as measured by the Cushing's QOL and SF-12v2 over time	
9. To evaluate the safety profile of pasireotide alone or in combination with cabergoline	9. Toxicity will be assessed using the National Cancer Institute-Common Toxicology Criteria Adverse Events version 4.03 (NCI-CTCAE v4.03) and for laboratory assessments that include biochemistry, hematology, urinalysis; special safety assessments that include the regular monitoring and recording of blood glucose, insulin, HbA1c, GH and IGF-1, thyroid and liver function tests, gallbladder examinations and ECGs. Concomitant medications/Significant nondrug therapies will be assessed from study enrollment until the safety follow-up visit.	
Other secondary	Not applicable	

[figure not shown]

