If patient cannot increase from 0.6mg twice a day to 0.9mg twice a day due to safety, and is not yet biochemically controlled, combination with cabergoline 0.5mg qd can be initiated right away with pasireotide at 0.6mg twice a day (see [Table 6-2](#)).

If patient is being escalated to 0.9mg twice a day, but cannot tolerate the dose, dose should be reduced to 0.6mg twice a day. If the latter dose does not lead to biochemical control, combination with cabergoline as described above can be initiated (see [Table 6-2](#)).

If combination pasireotide and cabergoline 0.5mg once a day is not tolerated, the dose of cabergoline can be reduced to 0.5mg every other day. If 0.5mg every other day is not tolerated, and biochemical control is not achieved, patient should be considered for discontinuation if no clinical benefit is derived (see [Table 6-2](#)).

If combination pasireotide and cabergoline 1.0mg once a day is not tolerated, the dose of cabergoline can be reduced to 1.0mg every other day. If 1.0mg every other day is not tolerated, and biochemical control is not achieved, patient should be considered for discontinuation if no clinical benefit is derived (see [Table 6-2](#)).

The minimum treatment of any regimen is 8 weeks. Patients losing biochemical control at any time point after the 8 week period will have the dose of the study medication increased immediately to the next level provided that the dose is well tolerated.

For patients whose starting dose is 0.6mg pasireotide twice a day monotherapy, at weeks 9, 18 and 27, before patient's UFC results are available, the investigator may select one of the following two options to dispense study medication to the patient for the next 5-9 weeks of treatment:

Option 1: The investigator dispenses study medication at the current dose, plus study medication at the next dose level at the end of week 8, 13, 17, 22, 26, or 31 visits. When patient's UFC results are available, the investigator should phone the patient to inform him/her to either remain at the current dose or titrate up to the next monotherapy dose level or start the combination therapy.

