#### **10.3.1 Safety objectives**

##### **10.3.1.1 Analysis set and grouping for the analyses**

For all safety analyses, the safety set will be used. Key safety analyses will be presented for patients who receive pasireotide in combination with cabergoline after they started receiving the combination therapy.

The overall observation period will be divided into three mutually exclusive segments:

1. pre-treatment period: from day of patient's informed consent to the day before first dose of study medication
2. on-treatment period: from day of first dose of study medication to 28 days after last dose of study medication
3. post-treatment period: starting at day 28+1 after last dose of study medication.

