##### **10.3.1.2 Adverse events (AEs)**

Summary tables for adverse events (AEs) have to include only AEs that started or worsened during the on-treatment period, the **treatment-emergent** AEs. However, all safety data (including those from the pre and post-treatment periods) will be listed and those collected during the pre-treatment and post-treatment period are to be flagged.

The incidence of treatment-emergent adverse events (new or worsening from baseline) will be summarized by system organ class and or preferred term, severity (based on NCI-CTCAE v4.03 grades), type of adverse event, relation to study treatment. Similar summaries will also be produced for treatment-emergent AEs of special interest. The number and percentage of patients with at least one treatment-emergent Adverse Event of Special Interest will be reported.

Deaths reportable as SAEs and non-fatal serious adverse events will be listed by patient and tabulated by type of adverse event and treatment regimen.

Specific safety event categories (SEC) will be considered. Such categories consist of one or more well-defined safety events which are similar in nature and for which there is a specific clinical interest in connection with the study treatment(s).

For each specified SEC, number and percentage of patients with at least one event part of the SEC will be reported.

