6.1 Treatment regimen

The following labels for treatment regimens will be used in generating tables and figures where is applicable:

- Pasireotide s.c alone
- Pasireotide s.c. in combination with cabergoline

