6.4.1.1 Dose intensity and exposure - Core and extension phase

Duration of exposure will be summarized by appropriate descriptive statistics. The following definitions will be used:

Treatment start date: defined as the first date at which a non-zero dose of cabergoline is administered during the study and recorded on the Dosage Administration Record (DAR) eCRF over core and extension phase for safety set.

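### SAP 6.6 and 6.6.1 do not carry over the combination-period safety analysis that Protocol 10.3.1.1 requires, and the SAP 6.1 regimen labels have no rule for assigning adverse events

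*SAP*

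**What the plan says.** The protocol makes two commitments on how safety is to be grouped.

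- Section 10.3.1.1: "Key safety analyses will be presented for patients who receive pasireotide in combination with cabergoline after they started receiving the combination therapy". This fixes both a population and a starting point. The same section defines the on-treatment period as running from the first dose to 28 days after the last dose of study medication.
- Section 10.3.1.2: deaths and non-fatal serious AEs are to be listed and "tabulated by type of adverse event and treatment regimen".

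Secondary objective 9 in Table 3-1 reads: "To evaluate the safety profile of pasireotide alone or in combination with cabergoline".

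The SAP sets a single frame for safety. Section 6.6 states: "All the safety analysis will be over core and extension phase combined based on safety set". Section 6.6.1 then names nine selections of treatment-emergent AEs, to be "listed and summarized for safety set from study start to final cut-off date for safety set", and says that incidence is given for the core phase and for the overall on-treatment period.

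Two other SAP sections bear on the point. Section 6.1 gives one label for pasireotide alone and one for the combination: "The following labels for treatment regimens will be used in generating tables and figures where is applicable". Section 6.4.1.1 sets a cabergoline start date, "defined as the first date at which a non-zero dose of cabergoline is administered during the study", and uses it for cabergoline exposure and dose intensity.

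**The concern.** The protocol asks for a safety summary that starts when cabergoline is added. The final SAP, which governs the combined core and extension analysis, describes AE tables that start at the first study dose and cover every treated patient. A programmer who follows 6.6 and 6.6.1 as written would produce no AE incidence for the period on the combination.

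This matters because cabergoline is added only when pasireotide alone has not controlled cortisol. Most patients who reach the combination have therefore already spent time on monotherapy. Unless events are dated against the first cabergoline dose, the AE burden of the combination cannot be read from the tables. Nothing in the primary efficacy analysis depends on this.

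**Working it through.** The plan states no figure that needs reproducing. The check is a comparison of texts, followed by a simple gauge of size.

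**Step 1. Requirement against specification.**

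| Element | Protocol 10.3.1.1 and 10.3.1.2 | SAP 6.6 and 6.6.1 |
|---|---|---|
| Population | Patients receiving the combination | Whole safety set |
| Start of counting | Start of the combination | Study start |
| Other windows | None needed | Core phase; overall on-treatment period |
| Deaths and serious AEs | By treatment regimen | No regimen split stated |

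No item in 6.6.1 restricts the tables to combination patients, starts the count at the first cabergoline dose, or assigns events to the regimen at onset.

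**Step 2. Do the 6.1 labels close the gap?** The labels could be applied in three ways, and the SAP does not choose among them.

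- Not applied to AE tables: one pooled column, with no combination incidence.
- Applied by patient (ever given cabergoline or not): the combination column includes each patient's earlier monotherapy events. The other column holds only patients who never received cabergoline, because they were controlled on pasireotide or stopped before it was added. The columns then differ by response as well as by treatment.
- Applied by regimen at onset: this would come close to what 10.3.1.1 asks, but it needs a date rule, which 6.1 and 6.6.1 do not give.

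**Step 3. Size.** The gauge is the share of the core phase spent on pasireotide alone:

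share = week of first cabergoline ÷ 35

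Inputs:

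- Core treatment lasts 35 weeks (Protocol 6.2.2).
- For patients starting on 0.6 mg twice daily, titration periods of one week begin at weeks 8, 17 and 26 (Protocol 4.1). Dispensing decisions fall later: "For patients whose starting dose is 0.6mg pasireotide twice a day monotherapy, at weeks 9, 18 and 27" (Protocol 6.4.1).
- On the standard path, cabergoline follows the 0.6 mg and 0.9 mg steps, so it starts at about week 17 to 18.
- If 0.9 mg cannot be given for safety reasons, cabergoline may follow the 0.6 mg step directly (Protocol 6.4.1), at about week 8 to 9.
- Patients entering on maximal tolerated pasireotide start cabergoline at study entry (Protocol 4.1), at week 0.

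Results:

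- Standard path: 17/35 = 48.6% and 18/35 = 51.4%, so about 49–51%.
- 0.9 mg not possible: 8/35 = 22.9% and 9/35 = 25.7%, so about 23–26%.
- Entering on maximal tolerated pasireotide: 0/35 = 0%.

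Protocol 10.5 plans for at most 6 patients of this last kind among 64. The documents do not say how many of the others reach cabergoline, so no overall share is calculated.

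**The case against.** A reader might infer that no planned AE table isolates the combination at all. The documents do not support going that far. The protocol itself plans these analyses, its section 10 describes the SAP as adding detail to the protocol methods, and nothing in SAP 6.6 expressly withdraws 10.3.1.1. The 6.1 labels could be applied to AE tables, and they could be applied by regimen at onset. SAP section 6 is also headed as relating to outputs that already exist. The core-phase SAP (reference [4]) and the SAP section 8 that the plan cites are not available here, and either could hold the missing rule. All of this stands, and it limits the point to an analysis that the final SAP does not specify. It does not remove the mismatch: 6.6 puts all safety analysis in one frame, 6.6.1 starts its count at study start, and 6.6.1 does not refer to [4] for assigning AEs.

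It can also be said that objective 9 does not by itself demand separation. The primary objective uses the same phrase for one overall stepwise regimen, so a pooled safety profile is a fair reading. That is accepted; the requirement rests on 10.3.1.1 and 10.3.1.2 alone.

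Finally, the study is exploratory, open-label and non-comparative, and onset dates and dosing dates are collected, so the tables can still be made. That lowers the severity and makes the correction cheap. It is not a reason to leave a stated protocol analysis out of the final plan.

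**Conclusion.** The point holds as a gap between protocol and SAP. SAP 6.6 and 6.6.1 do not specify the combination-period safety analysis in Protocol 10.3.1.1, and the 6.1 labels lack a rule for events in patients who change regimen. It should be corrected, with medium confidence because of the two sources not available.

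The percentages in the working are shares of core-phase time. A reader might take them as the amount by which combination AE incidence would be overstated. The documents do not support that: they give no event rates over time and do not say which column layout would be used. The shares equal the fraction of a patient's core-phase events that began before cabergoline only if the event rate is constant and the patient completes 35 weeks. They also do not apply unchanged to the combined core and extension tables, where longer follow-up makes the monotherapy share smaller. Individual timing will vary, because dose reductions and later loss of control can shift the week in which cabergoline starts.

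**What to change.** If the core-phase SAP or SAP section 8 already has an assignment rule, add one cross-reference in 6.6.1 extending it to the final analysis. If not, add to 6.6.1:

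- (a) A combination period, from the cabergoline start date already defined in 6.4.1.1 to 28 days after the last study dose.
- (b) The key AE tables (all, drug-related, serious, leading to discontinuation, special interest) for patients with at least one cabergoline dose, counting only events that started or worsened in that period.
- (c) Deaths and serious AEs tabulated by regimen at onset, to meet Protocol 10.3.1.2.

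Label (a) to (c) as protocol-specified but written after database lock. A table for the monotherapy period and patient-years beside the counts would be useful, but they are optional descriptive additions that the protocol does not specify, and should be labelled so.

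The cost is one paragraph and one derived flag comparing AE onset date with cabergoline start date. The SAP's own addendum of 27 October 2019 is a precedent: it added the Karnofsky status analysis after database lock because the protocol contained it and the SAP had missed it. The downside is a set of repeated tables with smaller denominators. The two periods are also sequential and not comparable arms, so the results should only be described.
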